 1. Intralipid will be started on day 1 of parenteral nutrition at 1g/kg/d

2. Intralipid dose will be maintained at 1g/kg/d while enrolled in the study and receiving parenteral nutrition, unless other clinical concerns arise as documented by primary team.
 - a. If further caloric intake is required, Intralipid may be increased at the discretion of the treating faculty based on the needs of the individual patient.
- ii. Other parenteral nutrition components:
 1. Amino acid will be provided to meet estimated protein requirements only and will not be increased as a form of caloric intake.
 - a. Term infant approximate goal of 3 g/kg/day and preterm infant approximate goal of 3.5 – 4 g/kg/day.
 2. Glucose infusion will be utilized and advanced per standard protocol to provide remainder of estimated non-protein caloric need of each individual patient.
 - a. Maximum glucose infusion rate (GIR) while enrolled in study of 16 mg/kg/min. If further caloric intake is required, Intralipid will be increased at the discretion of the treating faculty based on needs of the individual patient.
3. All Study Patients:
 - a. Enteral feedings:
 - i. Enteral breast milk or formula choice will be at the discretion of the primary faculty physician and advanced per physician practice.
 - b. Anthropometric Measurements:
 - i. Each group will have growth monitored per standard protocol with daily weights and weekly head circumference (OFC) and length.
 - ii. Weekly measurements used for research purposes will include weekly weight, length, and OFC as documented directly by the research team (primary investigators or same registered dietician).
 - iii. Corrected measurements will also be documented with weight, length, and OFC documented at 36 weeks (+/- 3 days) corrected gestational age.
 - iv. Follow-up measurements at 2 – 3 weeks after stopping study lipid or time of discharge, whichever comes first.
 - v. At each time point, anthropometric measurements will be replicated in triplicate and the average value for that measurement will be reported within the study.
 - vi. In the event of safety concerns to the patient or research team, as raised by the research team, patient care team, or regulatory entities, the study measurements will be conducted by the bedside patient nurse. These measurements will include length board use.

- c. Diagnoses associated with Prematurity:

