2. Lipid infusion will be held if triglyceride level > 400 mg/dL
 - a. Once triglyceride level <400 mg/dL lipid infusion can be restarted. A lower dose can be used if deemed necessary by the primary care team and dietitian.

viii. Bleeding studies

1. Platelets will be monitored once weekly until stable (minimum 2 consistent values, 5-7 days apart) and then once every 4 weeks.
2. INR will be measured once weekly until stable (at least 2 consistent values, 5-7 days apart) and then once every 4 weeks.
 - a. Blood volume 1.7 mL
 - b. Because this lab is not standard of care, the cost will be covered by research funds, not by the individual patient.

ix. Glucose will be monitored at initiation of parenteral nutrition until stable and then with significant changes in glucose infusion rate. This can be performed via basic metabolic profile (BMP), point of care (POC) glucose, or any other lab source that provides a blood glucose measurement.

1. If the blood glucose is >200 mg/dL on more than one measurement separated by at least 3 hours, the primary team will consider decreasing the patient's GIR.
2. If blood glucose is <50 mg/dL the primary team will consider increasing the GIR.

x. Blood volume:

1. Minimum blood volume per each phlebotomy event are listed in Table 2.
2. Total minimum blood volume 24.4 mL per patient over the 14 blood draws during the study.

xi. Post-study monitoring:

1. As indicated in Table 2, triglyceride, hepatic function panel, GGT, essential fatty acid panel, platelet count, and INR will be measured 2-3 weeks post-study completion or at time of discharge, whichever comes first.
 - a. This time frame will be for all patients enrolled in the study, regardless of their length of time within the study.
 - b. If the patient is to be discharged from the hospital prior to this 2-3 week time period, labs will be drawn within 3 days of discharge, prior to leaving the hospital.

Table 2: Minimum laboratory requirements while enrolled in study (TG= triglyceride, HFP = Hepatic Function Panel, FB = fractionated bilirubin, GGT= gamma glutamyl transferase, EFA = essential fatty acids, PLT= platelet count) (Blood volume is minimum required to perform all tests listed)

	Week													
	0	1	2	3	4	5	6	7	8	9	10	11	12	+2-3
Test	TG	TG	TG	TG	TG	TG	TG	TG	TG	TG	TG	TG	TG	TG
	HFP	FB	HFP	FB	HFP	FB	HFP	FB	HFP	FB	HFP	FB	HFP	HFP
	GGT		GGT		GGT		GGT		GGT		GGT		GGT	GGT
					EFA				EFA				EFA	EFA
	PLT	PLT			PLT			PLT					PLT	PLT
	INR	INR		INR			INR				INR		INR	INR

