Adverse events are defined using the Common Terminology Criteria for Adverse Events (CTCAE) version 4.0. Modifications to these definitions may be made if inappropriate for the neonatal patient population. Some specific events and definitions are listed in Table 3 below. This table does not include the CTCAE v4.0 grade 5, as this is defined as death in a patient. Therefore, any death of a patient will be defined as grade 5, irrelevant of the specific diagnostic category within CTCAE v4.0 or listed below.

Table 3: Definition of Specific Adverse and Serious Adverse Events

Event	Mild (Grade 1)	Moderate (Grade 2)	Severe (Grade 3)	Life Threatening (Grade 4)
Definition of adverse event	Mild transient symptoms only	Moderate illness or condition with	Severe illness or condition	Life threatening illness or

	monitored or symptomatic treatment. Aware of symptom but tolerated and no functional interference	new or significant altered treatment, causes some interference with normal activity or care.	unresponsive to medical treatment, incapacitating with inability to perform usual activity and interference with normal functions.	condition, required major surgery or respiratory support.
Hyperthermia (axillary temperature)	38.0-38.5 °C on single measurement	38.5-39.0 °C on single measurement	≥38.5 °C on two or more consecutive measurements	≥39.0 °C for two or more measurements despite environmental intervention or need for increased IV fluid volume
Pulmonary deterioration	Not applicable	FiO2 increase by 0.20-0.30 or new non-invasive ventilation or increase in MAP >3 during study drug infusion	FiO2 increase by 0.31-0.50 or new invasive ventilation or increase in MAP >5-7 during study drug infusion	FiO2 increase >0.50 or need for escalation in type of invasive ventilation or increase in MAP >7 during study drug infusion
Hypertension (defined as systolic blood pressure greater than the 95%ile for postmenstrual age)	Hypertension for less than a 24 hour period and no treatment needed	Hypertension 24-48 hours and no treatment needed	Hypertension for >48 hours or requiring treatment	Hypertension requiring multiple treatment types
Hyperglycemia	Transient glucose >180mg/dL for single determination with no further action taken	Glucose 180-250mg/dL for at least 2 determinations 6 hours apart	Glucose 251-350mg/dL for at least 2 determinations 6 hours apart or need for insulin or change in IV fluid	Glucose >350mg/dL, change in mental status, diuresis or dehydration

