Hypoglycemia	Transient glucose <50mg/dL on single measure	Glucose <50mg/dL on repeated measures, responds to treatment with	Glucose <40mg/dL on repeated measures or need for multiple dextrose boluses or need	Glucose <40mg/dL with change in mental status, seizures, glucose

		single intervention	for change in IV glucose infusion to >10mg/kg/min	unresponsive to glucose infusions, or need for glucagon or steroids
Elevated liver enzymes (AST and/or ALT)	1.5-2.0x normal (90-125 U/L)	2.1-4.0x normal (126-245 U/L)	4.1-10.0x normal (246-600 U/L)	>10.0x normal (>600 U/L)
Hypertriglyceridemia	150-250 mg/dL	250-500 mg/dL	500-1000 mg/dL	>1,000 mg/dL
Elevated creatinine (at >72 hours of age or older)	1.3-1.8 mg/dL	1.9-2.3 mg/dL	2.4-3.4 mg/dL	≥ 3.5mg/dL
Oliguria (urine output (UO) over 24 hour period)	UO <1.0 mL/kg/h	UO 0.5-1.0 mL/kg/h	UO <0.5 mL/kg/h	UO <0.3 mL/kg/h
Anemia (based on laboratory value)	Hct <34%	Hct <28%	Hct <24%	Hct <20% and/or cardiovascular instability from the anemia
Thrombocytopenia (platelet counts in 1000/cumm)	75-100	50-75	25-50 with no bleeding	<10 and/or bleeding
Coagulation study abnormalities	INR 1.5-2.0	INR 2.0-2.5	INR >2.5 with no clinically significant bleeding	INR >3.0 and/or >2.5 with clinically significant bleeding
Thrombosis (thrombus confirmed with imaging and radiographic report)	Non-inclusive thrombus with no associated symptoms.	Non-inclusive thrombus but with symptoms such as edema.	Thrombus leading to need for anticoagulation therapy but with no organ compromise.	Need for anti-coagulation therapy with compromise of extremity or organ related to thrombus.
Neutropenia (Absolute neutrophil count)	1600-2000	1000-1599	500-999	<500
Mental status	Mild irritability, possibly within normal range	Persistently irritable and/or intermittent lethargy	Lethargy, stupor, still arousable, single seizure	Non-responsive, need for respiratory intervention due to change

Systemic infection (including sepsis and/or bacteremia with positive blood culture)	Positive blood culture but not treated (felt to be contaminant)	Treated ≥ 5 days of consecutive antibiotics, antivirals or antifungals with no cardiovascular instability.	Treated for systemic symptoms, including cardiovascular instability and ≥ 5 days of antimicrobial with response to treatment.	Treated for systemic symptoms, including cardiovascular instability and ≥ 5 days of antimicrobial no or slow response to treatment.
---	---	---	--	--

Criteria for Stopping Study

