1) Individual Patient Stopping Criteria:

- a) Development of progressive cholestasis as defined by direct bilirubin of 3 mg/dL or greater on two separate lab draws 5 to 7 days apart.
- b) Clinically significant laboratory abnormalities that change the clinical course of the patient, or the patient's care and are deemed related to the study drug by the primary investigators ([name] or [name]). The laboratory abnormalities include, but are limited to:
 - i) Change in liver function with AST or ALT greater than 5 times the upper limit of normal or GGT greater than 3 times the upper limit of normal for patient age.
 - ii) Creatinine greater than 2 times upper limit of normal for patient age.
 - iii) Clinically significant coagulopathy with INR greater than 2.5 or INR greater than 1.5 and clinically significant bleeding.
 - iv) Clinically significant thrombocytopenia with platelet count less than 30 or less than 50 with bleeding.
 - v) Persistent hyperglycemia with glucose greater than 200 mg/dL despite changes in parenteral nutrition glucose infusion rate.
 - (1) Inability to tolerate appropriate calorie intake due to elevated glucose infusion rate that may be required with lipid reduction.
 - vi) Persistent hypertriglyceridemia (on 3 or more lab draws each at least 24 hours apart) greater than 250 mg/dL despite decreasing or holding lipid dose.
- c) At the request of the parent or legal guardian.
- d) At the request or recommendation of the patient's primary physician and care team.

If the patient is withdrawn from the study, treatment including parenteral nutrition administration and macronutrient content will be provided at the discretion of the primary faculty physician providing patient care.

2) Study Stopping Criteria:

- a) DSMC or primary investigator initiated study cessation:
 - i) As noted a Data Safety and Monitoring Committee (DSMC) of experts from Neonatology, Gastroenterology, Surgery and Statistics will meet within 2 weeks of the first 10 subjects and following at least every six months during the remainder of the study period. They will review patient recruit, patient outcomes, and adverse events in both prospective patient populations. Significant patient safety concerns will

be determined by the DSMC. These patient concerns include, but are limited to, finding a significant amount of AE or SAE within one study group or a large difference in outcomes between study treatment arms.

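### Table 3's absolute 10 mg/kg/min criterion can grade the same low glucose reading and infusion step as Grade 1 in one arm and Grade 3 in the other

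*Combined protocol and SAP*

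**What the plan says.** **Hypoglycaemia grading (Table 3).** Grade 1 is "Transient glucose <50mg/dL on single measure". Grade 3 has three alternatives: "Glucose <40mg/dL on repeated measures or need for multiple dextrose boluses or need" "for change in IV glucose infusion to >10mg/kg/min". The last of these is an infusion rate, not a glucose value.

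**Hyperglycaemia grading (Table 3).** Grade 3 is "Glucose 251-350mg/dL for at least 2 determinations 6 hours apart or need for insulin or change in IV fluid". No infusion-rate threshold appears in this row. Grade 1 is a single value above 180 mg/dL that prompts no action. Grade 2 is 180-250 mg/dL on two determinations six hours apart.

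**How GIR is set (Study Procedures, items 1.c and 2.a.ii).** In both arms glucose makes up the non-protein calories that lipid does not supply, with the same ceiling: "Maximum glucose infusion rate (GIR) while enrolled in study of 16 mg/kg/min". Lipid is advanced to a goal maximum of 3 g/kg/d in the Smoflipid arm and held at 1 g/kg/d in the Intralipid-reduction arm, where it may be raised at the treating faculty's discretion. The individual stopping criteria (item 1.b.v) acknowledge that lipid reduction may call for an elevated GIR.

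**Prompts to act (Study Procedures, item 3.e.ix), the same for all patients.** "If blood glucose is <50 mg/dL the primary team will consider increasing the GIR". At the other end, "If the blood glucose is >200 mg/dL on more than one measurement separated by at least 3 hours, the primary team will consider decreasing" the GIR.

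**Use of AE data.** AE and SAE rates by group are secondary objective 2.h. Under the study stopping criteria, the safety committee's concerns include "finding a significant amount of AE or SAE within one study group or a large difference in outcomes between study treatment arms". The trial is unblinded.

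**The concern.** A severity grade that is compared between arms should mean the same thing in each. Here one route to Grade 3 hypoglycaemia is an absolute GIR inside the range both arms may use, and the assigned lipid dose helps determine where an infant sits relative to it. Two infants with the same reading and the same response can then receive different grades because of their allocation.

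The hyperglycaemia row raises a related but separate problem. A GIR reduction that the protocol itself asks the team to consider may count as a change in IV fluid. If so, values in the Grade 2 band become Grade 3 because of a decision made by an unblinded team.

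At stake is the reading of severity by arm. The committee's first review comes after only 10 patients, with enrolment on hold, so a few relabelled events could carry weight.

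**Working it through.** The plan gives no GIR figure by arm, so there is nothing of its own to reproduce. The check is an energy balance.

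**Inputs from the protocol:** lipid 3 v 1 g/kg/d; amino acids about 3 g/kg/d (term) to 3.5-4 g/kg/d (preterm); GIR ceiling 16 mg/kg/min; grade boundary 10 mg/kg/min.

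**Assumptions, not in the protocol:** lipid 9-10 kcal/g, dextrose 3.4-4.0 kcal/g, protein 4 kcal/g, and equal parenteral calories in both arms.

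**Step 1: GIR gap.** Gap = (lipid difference × kcal/g lipid) ÷ kcal/g dextrose × 1000/1440.
- 3 v 1 g/kg/d, low end: 2 × 9 ÷ 4.0 × 1000/1440 = 3.1 mg/kg/min.
- 3 v 1 g/kg/d, high end: 2 × 10 ÷ 3.4 × 1000/1440 = 4.1 mg/kg/min.
- 2 v 1 g/kg/d: 1.6-2.0 mg/kg/min.
- 1 v 1 g/kg/d (first day, or late weaning): 0.

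**Step 2: same reading, same step.** Take lipid at 10 and dextrose at 3.4 kcal/g, so 1 mg/kg/min of glucose is 3.4 × 1.44 = 4.896 kcal/kg/d. One reading of 45 mg/dL is answered by a GIR rise of 1 mg/kg/min.
- Case A, 70 kcal/kg/d non-protein: Smoflipid (70 − 30)/4.896 = 8.2, rising to 9.2. Reduced Intralipid (70 − 10)/4.896 = 12.3, rising to 13.3.
- Case B, 76.5 kcal/kg/d non-protein: Smoflipid (76.5 − 30)/4.896 = 9.5, rising to 10.5. Reduced Intralipid (76.5 − 10)/4.896 = 13.6, rising to 14.6.

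| | Any increase ending above 10 counts | Only crossing 10 counts |
|---|---|---|
| Case A, Smoflipid / reduced Intralipid | Grade 1 / Grade 3 | Grade 1 / Grade 1 |
| Case B, Smoflipid / reduced Intralipid | Grade 3 / Grade 3 | Grade 3 / Grade 1 |

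Each reading of the wording produces an arm difference, in opposite directions. If the readings below 50 were repeated and responded to a single intervention, the lower grade would be Grade 2, not Grade 1.

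**Step 3: when the arms straddle 10.** Total parenteral energy at which GIR equals 10 is 48.96 + 10 × lipid + 4 × amino acids.
- Amino acids 3 g/kg/d: 48.96 + 10 + 12 = 71.0 (lipid 1) and 48.96 + 30 + 12 = 91.0 (lipid 3).
- Amino acids 4 g/kg/d: 75.0 and 95.0.

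So the straddle runs over about 71-91 or 75-95 kcal/kg/d. Table 1 pairs 50-60% of calories from parenteral nutrition with 40-50 enteral kcal/kg/d, which implies a total near 100. At 100 kcal/kg/d on full parenteral nutrition with lipid 3, GIR is (100 − 30 − 16)/4.896 = 11.0 to (100 − 30 − 12)/4.896 = 11.8, so both arms exceed 10. Below about 71 kcal/kg/d, neither arm reaches 10 at baseline.

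**Step 4: hyperglycaemia.** Two values of 205 mg/dL three hours apart satisfy the prompt to consider a GIR cut. If a cut counts as a change in IV fluid, the event is Grade 3 in either arm. The values lie in the Grade 2 band and, at three-hour spacing, do not strictly meet even Grade 2.

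**Scale.** The plan names Fisher's exact test for categorical outcomes but does not say it will be applied by grade. If it were (two-sided), 5/25 v 0/25 Grade 3 or worse gives p = 0.050, 6/25 v 0/25 gives 0.022, and 5/12 v 0/12 gives 0.037.

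**The case against.** **Grade has no formal role.** The plan tabulates the proportion with adverse events, not by grade, and the SAE definition does not refer to grade. A single reading below 50 mg/dL is already a Grade 1 AE, so the any-AE comparison is unchanged. This stands, and it limits the harm to severity summaries and judgements of imbalance.

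**The mechanism is conditional.** The GIR rule and ceiling are shared, the protocol says only that a higher GIR may be needed, Intralipid can be raised, and the arms straddle 10 over a limited energy range. This also stands. Even so, with a total near 100 kcal/kg/d, the 71-95 band falls within Table 1's rows for 60-100% parenteral calories, where Smoflipid is 3 g/kg/d.

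**Intervention-based grading is common, and GIR is recorded anyway.** Table 3 also grades hypertension, thrombosis and infection partly by treatment, and parenteral nutrition characteristics will be tabulated. But GIR is part of what differs between these arms, and weekly summaries would not show the GIR at the event.

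**Stronger readings the documents do not support.** A reader might infer that the hyperglycaemia row is biased by arm in the same way. It is not: with no rate threshold, the same reading and action get the same grade at any baseline GIR, and more hyperglycaemia at a higher GIR would be a real effect of the strategy. A reader might also infer that the wording must inflate severe events in the reduction arm. That holds only if any increase ending above 10 counts; if only crossing counts, the bias within the straddle reverses.

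**Conclusion.** The hypoglycaemia point holds. On either reading of the 10 mg/kg/min wording the grade depends on baseline GIR, which the assigned lipid dose influences by about 3.1-4.1 mg/kg/min at 3 v 1 g/kg/d. This rests on equal parenteral calories and the assumed calorie values. The direction cannot be stated until the wording is defined, and the arms straddle 10 only at about 71-95 kcal/kg/d of parenteral nutrition (lipid 10, dextrose 3.4, protein 4 kcal/g; amino acids 3-4 g/kg/d).

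For hyperglycaemia the defect is narrower: an unblinded management decision can raise the grade, with no built-in arm difference. The effect is on severity comparisons and safety committee review, not on the proportion with any AE. It should be corrected, but it does not threaten the primary objective.

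**What to change.** For both glucose events, assign the severity grade used in arm comparisons and committee reports from glucose value, repetition and symptoms. Tabulate interventions (GIR or fluid change, boluses, insulin) and the GIR at the event separately, by arm.

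Deleting the two intervention criteria alone would not do. The 205/205 example, once acted on, would meet no grade, and the adverse event section counts laboratory abnormalities as AEs only if they meet the table's criteria. So keep as an AE every event that now meets any Table 3 criterion, and adjust the Grade 1 and Grade 2 wording so none drops out. The conditions to revisit are no action taken (hyperglycaemia Grade 1), six-hour spacing (hyperglycaemia Grade 2) and response to a single intervention (hypoglycaemia Grade 2).

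The cost is a rewording of the two Table 3 rows, slightly more tabulation, and fewer events graded 3. No dose or treatment rule changes.

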 - i. Each patient's chart will be reviewed for documentation of retinopathy of prematurity or bronchopulmonary dysplasia (chronic lung disease). The absence or presence of these diseases at the time of discharge will be noted for each study patient, particularly those patients born prematurely at less than 37 weeks gestation.
- d. Length of Stay:
 - i. An ICU length of stay will be calculated for each patient based on their admit date and discharge date from the Riley NICU.
 - ii. For patients transferred to another unit prior to discharge the transfer date will also be documented. For these patients a NICU length of stay and total hospital length of stay will be calculated.
- e. Laboratory monitoring (see Table 2 below for reference schedule):
 - i. Effort will be made to draw all study lab tests along with other standard of care, routinely scheduled labs.
 - ii. The schedule outlined here is a schedule of minimum laboratory work to be obtained. These studies may be obtained more often by the patient's primary clinical team. Any lab test obtained by the primary team within 3 days for weekly labs or within one week for less frequent labs will be used in place of the research lab test.
 - iii. Of note all lab tests listed could be considered standard of care, with the exception of INR.
 - iv. Essential fatty acid profiles will be obtained every 4 weeks (28 days) while receiving study lipid regimen.
 - 1. Blood volume needed 0.3-1mL
 - 2. Considered standard of care in any patient on alternative lipid dosing, such as patients enrolled in this study.
 - 3. If diagnosed with essential fatty acid disorder, defined as triene:tetraene ratio >0.05:
 - a. If Smoflipid dose is less than 3 g/kg/d, SMOF will be increased by 0.5 g/kg/d or to 3 g/kg/d maximum
 - b. Those receiving Smoflipid at 3 g/kg/d will be changed to Intralipid at current Smoflipid dose
 - c. Those receiving Intralipid will have their dose increased by 0.5 g/kg/d to maximum of 3 g/kg/d
 - v. Total and fractionated bilirubin levels will be monitored at least once weekly (7 days)
 - vi. Liver function panel and gamma-glutamyl transferase (GGT) will be monitored at least every 2 weeks (14 days).
 - vii. Triglyceride levels will be monitored within the first 48 hours of lipid initiation and then once weekly (7 days).

1. If triglyceride level >250 mg/dL will decrease dose of study lipid by 1g/kg/d to minimum of 2 g/kg/d of Smoflipid or 1 g/kg/d three days per week for Intralipid

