All patients will be monitored on a daily basis for the development of any adverse events (AE) from the start of the study lipid until one week (7 days) after leaving the study. An adverse event is defined as any untoward medical occurrence in a research subject temporally associated with the use of the study drug, whether or not it is related to the drug. Any worsening of a pre-existing condition or illness is considered an adverse event. This includes pre-existing and or new clinical conditions or morbidities associated with prematurity or the patient's underlying diagnoses. Laboratory abnormalities or vital sign changes are considered adverse events only if they meet the specific criteria listed in the table below. A serious adverse event (SAE) is an AE that leads to death of a subject, life-threatening event, persistent or significant disability, or an important medical event requiring medical or surgical intervention to prevent a serious outcome.

Many possible AE and SAE are listed in Table 3 below. Patients will be monitored continuously by one of the principal investigators, [name] or [name], for possible AEs and SAEs. Clinical significance and relation to the study will be determined by [name] and/or [name] based on best medical judgement. Unanticipated events that are determined to be an AE related or possibly related to the research drug will be promptly reported to the IRB by [name] or [name] within 5 business days. Major protocol issues, including drug administration issues or errors, will also be reported to the IRB within 48 hours. Events that are determined to be an SAE or lead to death of a patient will be promptly reported to the IRB within 24 hours.

A separate Data and Safety Monitoring Committee (DSMC) will be used to monitor patient outcomes and AE along with SAE events. The DSMC members will not include the primary investigation team and will be made up of other experts from Neonatology ([name]), Pediatric General Surgery ([name]), Pediatric Gastroenterology ([name]), and Statistics. The DSMC will meet within 2 weeks following enrollment of the first 10 patients. Further enrollment will be put on hold pending initial DSMC review. If no safety concerns are found by independent DSMC review, patient enrollment will proceed. DSMC will meet subsequently every 6 months for the duration of the study.

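### Table 3 leaves a non-bleeding platelet count from 10 to below 25 without a grade, and the protocol does not say which text then decides whether it is an adverse event

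*Combined protocol and SAP*

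**What the plan says.** The thrombocytopenia row of Table 3 has four cells, in units of 1000/cumm: Grade 1 is 75 to 100, Grade 2 is 50 to 75, Grade 3 is "25-50 with no bleeding" and Grade 4 is "<10 and/or bleeding".

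Three other statements bear on a count that fits none of these cells:

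- The section on adverse and serious adverse events restricts laboratory events to the table: "Laboratory abnormalities or vital sign changes are considered adverse events only if they meet the specific criteria listed in the table below".
- The paragraph that introduces Table 3 says "Adverse events are defined using the Common Terminology Criteria for Adverse Events (CTCAE) version 4.0", allows modifications for neonates, and describes the table as partial: "Some specific events and definitions are listed in Table 3 below".
- The first row of Table 3 grades any event by its general severity. Its Grade 2 cell refers to an illness or condition with "new or significant altered treatment, causes some interference with normal activity or care".

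Rates of adverse and serious adverse events by group are secondary objective h. Statistical Considerations tabulates adverse events as proportions and compares categorical variables by Fisher's exact test at the 5% level. Study Stopping Criteria has the DSMC review adverse events for imbalance between the groups.

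**The concern.** A severity scale should not lose events as they become worse. Under the table-only rule for laboratory values, this row does: a non-bleeding count of 30 is a severe event, a count of 9 is life-threatening, and a count of 15 is not an event.

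Other readings are possible. An investigator could turn to CTCAE v4.0, or could use the general row if the count led to a change of treatment. The protocol does not say which text prevails, so the same count could be omitted, graded from CTCAE, or graded by judgement.

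What is at stake is the reliability of a tested secondary safety outcome that the DSMC also uses. The counts themselves stay in the laboratory data, but platelets are not among the continuous measurements named for tabulation. The adverse event table is therefore the only named analysis that would show thrombocytopenia. The trial is not blinded and the principal investigators assess events, so inconsistent handling could differ between arms.

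**Working it through.** **Coverage of the platelet row.** The four cells were applied as written to counts from 0 to 100.

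| Count (1000/cumm) | No bleeding | With bleeding |
|---|---|---|
| 9 | Grade 4 | Grade 4 |
| 10 | none | Grade 4 |
| 15 | none | Grade 4 |
| 24 | none | Grade 4 |
| 25 | Grade 3 | Grade 4 |
| 30 | Grade 3 | Grade 4 |

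Every whole number from 10 to 24 (24 − 10 + 1 = 15 values) is ungraded without bleeding. The gap does not exist when there is bleeding.

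**Other rows.** The value ranges of the nine numeric blood-test rows were compared: high glucose, low glucose, AST/ALT, triglycerides, creatinine, hematocrit, platelets, INR and neutrophils. Only the platelet row skips a band wider than rounding.

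Among the vital signs, the hyperthermia row has a smaller gap. Grade 2 ends at 39.0 °C for a single reading, and Grade 3 needs two or more consecutive readings. Grade 4 applies at 39.0 °C or more "for two or more measurements despite environmental intervention or need for increased IV fluid volume". A single axillary reading above 39.0 °C has no grade unless the fluid clause is met.

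**Comparison with the stopping criteria.** The individual patient stopping criteria include a clinically significant platelet count below 30, if it changes the course or care of the patient and is judged related to the study drug. All 15 ungraded values are below 30. A count can thus meet the platelet part of a stopping criterion and have no platelet grade.

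**Size for one infant.** Inputs are the target of 25 per arm and the minimum of 12 per arm. If an infant's only low counts lie in the gap, the arm's thrombocytopenia proportion changes by:

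- 1/25 = 4.0 percentage points
- 1/12 = 8.3 percentage points

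The lower bound is 0. An infant who also has a recorded count between 25 and 100 keeps a lower-grade event.

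**Effect on the test.** The plan does not state sidedness, so two-sided tests are assumed. For k events in one arm and 0 in the other, with n per arm, the two-sided Fisher p-value is 2 × C(n,k) / C(2n,k).

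| n per arm | Events | Calculation | p |
|---|---|---|---|
| 25 | 1 v 0 | 2 × 25 / 50 | 1.000 |
| 25 | 5 v 0 | 2 × 53,130 / 2,118,760 | 0.0502 |
| 25 | 6 v 0 | 2 × 177,100 / 15,890,700 | 0.0223 |
| 12 | 1 v 0 | 2 × 12 / 24 | 1.000 |
| 12 | 4 v 0 | 2 × 495 / 10,626 | 0.0932 |
| 12 | 5 v 0 | 2 × 792 / 42,504 | 0.0373 |

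One missed infant changes a 5% decision only when the arms are already near the boundary: 6 v 0 recorded as 5 v 0 at 25 per arm, or 5 v 0 recorded as 4 v 0 at 12 per arm. These counts illustrate the mechanism and are not expected results.

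**The case against.** The strongest reply is that the table-only rule is specific and the CTCAE sentence is general, so Table 3 governs laboratory values and the problem is one skipped band, a drafting slip. That reading is reasonable, but it does not rescue the row. It gives precisely the result that a count of 15 is no event. It also has to be inferred, because the protocol never ranks the two texts.

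A second reply is that the protocol protects these infants elsewhere, through the stopping criterion for counts below 30 and through platelet monitoring that continues weekly until values are stable. The laboratory schedule is moreover a minimum: "These studies may be obtained more often by the" primary clinical team. This has force on size. Repeat testing makes another recorded count of 25 to 100 plausible, and the infant would then still be counted at a lower grade. But the stopping criterion is conditional and supplies no adverse event grade.

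Third, the plan names no test specific to thrombocytopenia. If its adverse event outcome means any adverse event, an infant with another event changes nothing. This also stands, and the p-values above apply only if the row is analyzed separately.

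Fourth, the sentence on investigator judgement covers clinical significance and relation to the study, not grading, and a platelet count is objective. The possibility of different handling by arm is therefore a risk left open by an undefined rule. Nothing in the documents shows that it would occur.

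Lastly, serious adverse events are defined by outcome or need for intervention and not by grade. The gap therefore does not by itself decide whether an event is serious, although a serious event must first be an adverse event.

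**Conclusion.** The point holds. The platelet row is wrong as written: without bleeding, counts from 10 to below 25 have no grade, while counts on both sides do. The protocol does not settle whether such a count is omitted, graded from CTCAE v4.0 or graded under the general row.

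The consequence is bounded. The documents give no incidence, so the effect on adverse event rates cannot be computed and may be zero. The figures of 4.0 and 8.3 points assume an infant whose only low counts lie in the gap and a proportion reported for thrombocytopenia separately. One such infant cannot alone create or remove a significant difference. The primary cholestasis outcome is untouched. The gap should still be corrected, because it affects a secondary safety outcome that is tested between groups and reviewed by the DSMC. The temperature gap is minor.

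**What to change.** 1. Make the thrombocytopenia row contiguous so that every count at or below the Grade 1 limit has a grade. The clinical team and DSMC should set the boundary and reconcile the row with the platelet threshold in the individual stopping criteria. No cut-off is proposed here.
2. Add one sentence to the adverse event section saying how Table 3, the table-only rule for laboratory and vital sign changes, and CTCAE v4.0 relate when a value falls between bands.
3. In the same edit, close the gap for a single axillary temperature above 39.0 °C.

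The cost is a few table cells and one sentence, and possibly a few more reported adverse events.
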